### **5) Study Design**

#### **a) Recruitment Methods**

 Mount Sinai	Protocol Title:	A PLACEBO-CONTROLLED, DOUBLE-BLIND, RANDOMIZED, CROSS OVER PILOT STUDY OF THE EFFICACY AND TOLERABILITY OF INCOBOTULINUM TOXIN A (XEOMIN) AS A TREATMENT FOR FOCAL TASK-SPECIFIC DYSTONIA OF THE MUSICIAN'S HAND
	Principal Investigator Name/Contact Info:	[name].
	Primary Contact Name/Contact Info	[name] [contact]
	Date Revised:	10/22/2019
	Study Number:	HS: 13-00822 GCO: 13-1679

Patients will be recruited from the Faculty Practices of Drs. [name] and [name]. A majority of patient recruitment is anticipated through [name] practice. Furthermore, flyers will be posted throughout Mount Sinai Medical Hospital and NYU Hospital to increase the potential of recruitment of musicians diagnosed with dystonia and forwarded to musical training institutions, musical organizations and advocacy groups for patients with dystonia. IRB approval will be sought when the flyers are designed and the study team deems the need for this approach to increase study enrollment.

### **b) Inclusion and Exclusion Criteria**

Any adult patient is eligible for inclusion, provided they meet the following inclusion and exclusion criteria:

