#### INCLUSION CRITERIA:

- Patients with focal task-specific dystonia of one or both hands, selectively triggered by performance on a musical instrument.
- Patients must have been evaluated by [name] at the Movement Disorders Division of NYU Langone Hospital as part of their clinical care.
- Patients whose performance on an instrument is directly linked to their occupation.
- Patients must be between the ages of 18 and 80.
- Impairment in musical performance must be visible and demonstrable.

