### **c) Patients with a medical condition that precludes them from receiving BoNT injections. Number of Subjects**

This will be a placebo-controlled, double-blind, randomized, cross-over pilot study to assess the efficacy and tolerability of BoNT injections to treat musician's dystonia. The study will enroll a total of 2 patients that will be divided into two groups:

 Mount Sinai	Protocol Title:	A PLACEBO-CONTROLLED, DOUBLE-BLIND, RANDOMIZED, CROSS OVER PILOT STUDY OF THE EFFICACY AND TOLERABILITY OF INCOBOTULINUM TOXIN A (XEOMIN) AS A TREATMENT FOR FOCAL TASK-SPECIFIC DYSTONIA OF THE MUSICIAN'S HAND
	Principal Investigator Name/Contact Info:	[name].
	Primary Contact Name/Contact Info	[name] [contact]
	Date Revised:	10/22/2019
	Study Number:	HS: 13-00822 GCO: 13-1679

- 1) Group 1: Naïve to BoNT treatment (10 patients).
- 2) Group 2: Prior treatment with BoNT (10 patients).

The study anticipates screening 26 patients to enroll 21 who are eligible for randomization.

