## f) Procedures Involved in the Human Research

Every patient's dystonic movement disorder will be videotaped at each time point. The patient will bring in their instrument if possible; a keyboard will be provided for pianists. The patient will be encouraged to wear similar clothing/jewelry/nail polish etc. so each video recording will be identical at each time point.

The study will last a total of 24-28 weeks with the schedule as follows:

Visit 1- (Day 0) - Screening and baseline:

- Consent Form Process – completed prior to any research procedures
- Comprehensive Neurologic History and Physical Examination (MRC scales and dynamometry)
- Blood tests
- Patient's subjective rating scale of symptoms at baseline, HADS and perceived stress (questionnaires)
- Video of targeted hand(s) by [name] at NYU Langone medical center
- Selection of Muscles to inject – by [name] at NYU Langone medical center.
- Identification of the muscles and Injection of muscles

Visit 2 and Visit 3 will contain the following evaluations:

- Brief neurological exam to evaluate for weakness of the targeted muscles and surrounded non-targeted muscles (dynamometry, and MRC )
- Patient's subjective rating scale of symptoms, HADS and perceived stress (questionnaires)
- Assess for side effects
- Video of targeted hand(s) by [name] at NYU Langone medical center.
- Administer booster to patients who feel symptoms have not improved

Visit 4

 Mount Sinai	Protocol Title:	A PLACEBO-CONTROLLED, DOUBLE-BLIND, RANDOMIZED, CROSS OVER PILOT STUDY OF THE EFFICACY AND TOLERABILITY OF INCOBOTULINUM TOXIN A (XEOMIN) AS A TREATMENT FOR FOCAL TASK-SPECIFIC DYSTONIA OF THE MUSICIAN'S HAND
	Principal Investigator Name/Contact Info:	[name].
	Primary Contact Name/Contact Info	[name] [contact]
	Date Revised:	10/22/2019
	Study Number:	HS: 13-00822 GCO: 13-1679

- Brief neurological exam to evaluate for weakness of the targeted muscles and surrounded non-targeted muscles (dynamometry, MRC)
- Patient's subjective rating scale of symptoms, HADS and perceived stress (questionnaires)
- Assessment of side effects
- Video of targeted hand(s) Injection of muscles by [name] at NYU Langone medical center.

Visit 4a or 4b. This is optional visit at Week 6, 8 are depending on optimal dosing at weeks 2 and 4.

This visit will assess the improvement in musical performance. It will be 4 weeks after optimal booster injection.

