- Brief neurological exam to evaluate for weakness of the targeted muscles and surrounded non-targeted muscles (dynamometry, and MRC )
- Patient's subjective rating scale of symptoms and perceived stress (questionnaires)
- Assess for side effects
- Video of targeted hand(s) by [name] at NYU Langone medical center.

Visit 5; Week 12 (week 14 or 16 depending on previous dosing schedule) will contain the following evaluations:

- Brief neurological exam to evaluate for weakness of the targeted muscles and surrounded non-targeted muscles (dynamometry, and MRC )
- Patient's subjective rating scale of symptoms, HADS and perceived stress (questionnaires)
- Assess for side effects
- Video of targeted hand(s) (Groups 1 & 2 will be crossed over and will receive their 2nd injection cycle) by [name] at NYU Langone medical center.
- Treatment may be deferred for up to 2-4 weeks in any individuals who have persistent weakness from the first treatment cycle

 Mount Sinai	Protocol Title:	A PLACEBO-CONTROLLED, DOUBLE-BLIND, RANDOMIZED, CROSS OVER PILOT STUDY OF THE EFFICACY AND TOLERABILITY OF INCOBOTULINUM TOXIN A (XEOMIN) AS A TREATMENT FOR FOCAL TASK-SPECIFIC DYSTONIA OF THE MUSICIAN'S HAND
	Principal Investigator Name/Contact Info:	[name].
	Primary Contact Name/Contact Info	[name] [contact]
	Date Revised:	10/22/2019
	Study Number:	HS: 13-00822 GCO: 13-1679

Visit 6 and visit 7; Week 14 or 16 or 18 depending on previous dosing schedule will contain the following evaluations:

- Brief neurological exam to evaluate for weakness of the targeted muscles and surrounded non-targeted muscles (dynamometry, and MRC )
- Patient's subjective rating scale of symptoms, HADS and perceived stress (questionnaires)
- Assess for side effects
- Video of targeted hand(s) by [name] at NYU Langone medical center
- Administer booster to patients who feel symptoms have not improved

Visit 7a or 7b is optional visit which will be 4 week after optimal dosing injection.

- Brief neurological exam to evaluate for weakness of the targeted muscles and surrounded non-targeted muscles (dynamometry, and MRC )
- Patient's subjective rating scale of symptoms, HADS and perceived stress (questionnaires)
- Assess for side effects
- Video of targeted hand(s) by [name] at NYU Langone medical center

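### Entry criteria set no minimum time since the last clinical BoNT injection, although half the sample are prior users and Visit 1 is both baseline and first injection

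*Combined protocol and SAP*

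**What the plan says.** Section 5b opens with "Any adult patient is eligible for inclusion, provided they meet the following inclusion and exclusion criteria". The inclusion list covers the type of dystonia, evaluation by a named clinician "as part of their clinical care", occupational link, age, and severity: "Impairment in musical performance must be visible and demonstrable". The exclusion list removes patients whose dystonia does not interfere with playing and those with unstable conditions. A third exclusion has run into the heading of section 5c: "Patients with a medical condition that precludes them from receiving BoNT injections". No item states a time since the last BoNT injection.

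Section 5c plans two groups of 10, one BoNT-naive and the other "Group 2: Prior treatment with BoNT (10 patients". Section 5f makes Visit 1 (Day 0) both screening and baseline. It lists the neurologic history and examination with MRC and dynamometry, and ends with "Identification of the muscles and Injection of muscles". Section 5e defines the weakness outcome by comparison with the baseline visit.

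For its own doses the plan does allow time. Section 5f puts the second cycle at "Week 12 (week 14 or 16 depending on previous dosing schedule", and adds: "Treatment may be deferred for up to 2-4 weeks in any individuals who have persistent weakness from the first treatment cycle".

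**The concern.** The plan accepts that a study dose may still act 12 weeks or more after injection, and guards cycle 2 against that. Nothing comparable guards cycle 1 against a clinical dose given before the study. The exposure is plausible: Objectives says BoNT is often used in these musicians, and recruitment is through the practices of clinicians who treat focal dystonia.

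Two things are at stake. The first is tolerability, a stated aim. If a hand is already weak at Visit 1 and the old weakness then fades, the loss measured after study BoNT is too small. The second is efficacy: a residual dose would make a first placebo cycle partly active.

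**Working it through.** **Inputs from the documents.** N = 20, two-treatment crossover, within-patient SD 1, difference 0.935 units, two-sided 0.05, 80% power (statistical paragraph in section 5h); 10 prior users (5c); cycle 2 from week 12 (5f).

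**Assumptions, not in the documents.** k prior users carry a residual (range 3 to 10), split equally between the two orders. For strength, the residual is a fraction f of one study dose's weakening effect (25% to 50%). For efficacy, it is r units at the cycle 1 reading (0.25 to 0.5).

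**The plan's own figure.** SE = sqrt(2 × 1²/20) = 0.316. Noncentral t with 18 df gives 79.8% power at 0.935, so the stated 80% reproduces.

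**Weakness against Visit 1.** Let E be the true strength loss from study BoNT and w = fE the residual loss at Visit 1.

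- Residual gone by the reading: change on BoNT is −E + w, in either order. Mean understatement is k × f/20.
  - k = 3, f = 0.25: 3.75%
  - k = 5, f = 0.5: 12.5%
  - k = 10, f = 0.5: 25%
- Residual still present in cycle 1 and additive: a BoNT-first patient shows −(E + w) + w = −E, with no understatement. Only placebo-first patients are affected, so the last figure halves to 12.5%.

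**Weakness as BoNT cycle minus placebo cycle.** If the residual has gone by both readings, the changes are −E + w and +w. Their difference is −E, and the shared baseline error cancels exactly. If it persists additively in cycle 1, BoNT-first patients give −(E + w) and placebo-first patients −E + w, which average to −E over balanced orders. Only a persisting residual that is not additive leaves an error in this contrast.

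**Efficacy contrast, BoNT minus placebo.** Let d be the true difference and s the share of r that adds to study BoNT. A placebo-first patient gives d − r and a BoNT-first patient d + s × r. Mean shift over 20 patients = −(k/2)(1 − s)r/20.

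| Case | Mean shift | Power at 0.935 |
|---|---|---|
| No residual | 0 | 79.8% |
| Additive (s = 1), k = 3, r = 0.25 | 0 | 79.7% |
| Additive, k = 10, r = 0.5 | 0 | 77.4% |
| Nothing added (s = 0), k = 3, r = 0.25 | −0.019 (2.0%) | 78.2% |
| Nothing added, k = 5, r = 0.5 | −0.0625 (6.7%) | 74.2% |
| Nothing added, k = 10, r = 0.5 | −0.125 (13.4%) | 67.8% |

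In the additive rows the variance of a paired difference is 2 + (k/20)r², that is 2.009 and 2.125. In the s = 0 rows it is kept at 2.

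**Who could be exposed.** If an effect lasts 12 weeks, the Visit 1 baseline is exposed for anyone injected less than 12 weeks before entry. A reading at week 4 is exposed only for those injected less than 12 − 4 = 8 weeks before. The post-booster readings at weeks 6 and 8 are exposed only below 6 and 4 weeks.

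**The case against.** The strongest reply is that this is a placebo-controlled crossover, so an error in a baseline shared by both cycles drops out of the comparison that matters. That is right when the residual has gone by both readings. However, section 5e describes weakness only against the baseline visit, so the plan does not commit to the comparison that gives this protection.

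Second, the entry criteria do some of the work. Impairment must be visible and must interfere with playing, and Visit 1 includes a history, strength testing and expert muscle selection before injection. This makes full residual benefit unlikely. It does not exclude partial benefit, and leftover weakness is a different matter from dystonia. An examiner may choose to wait, but no rule requires it.

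Third, the larger figures need all 10 prior users to carry a large residual. For 67.8% power, each must retain 0.5 units at the reading, 53% of 0.935 (0.5/0.935), with nothing added by study BoNT, while still meeting the impairment criteria. This stands. The 25% and the 67.8% also cannot be taken together: the first assumes the residual has gone by the reading, the second that it is still there.

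Fourth, an entry rule comes late. From the 22 October 2019 revision to the end of June 2020 is about 36 weeks. Subtracting 24 to 28 weeks of participation leaves 8 to 12 weeks for entry. This stands, and shifts the weight of the remedy to data already collected.

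**Conclusion.** The gap is real and worth closing, but its size is unknown. As written, a recently injected patient can enter with a contaminated strength baseline and, if randomised to placebo first, a partly active placebo cycle. A reader might infer that half the sample is contaminated, that weakness will be understated by a quarter, or that power will drop to 68%. The documents support none of these. They give no interval since the last injection and no residual size, and prior treatment may mean years ago. The 25% and 67.8% figures are worst-case illustrations under different residual states, not expected consequences. Nor is the efficacy estimate necessarily biased: an additive residual causes no mean shift under balanced orders, and the smallest non-additive case costs 0.019 units. The firmer consequence is for weakness judged only against Visit 1, and a within-patient cycle comparison largely removes it.

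**What to change.** 1. For anyone still to enter, add to section 5b a minimum of 12 weeks since the last BoNT injection in the affected limb, with entry deferred 2 to 4 weeks if weakness persists. This mirrors the rule before cycle 2.
2. For all patients, make the BoNT-cycle versus placebo-cycle strength difference, at corresponding visits, the main weakness comparison. Report change from Visit 1 alongside. MRC and dynamometry are already listed at the visits in both cycles, so no new measurements are needed.
3. Before unblinding, take the date of the last pre-study injection from existing records. Report how many patients were under 12 weeks, by treatment order.
4. Keep everyone in the main efficacy comparison. An analysis without the under-12-week patients is supportive only: at 0.935 units, power is about 72% with 17 pairs (15 df) and 66% with 15 pairs (13 df).

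The cost is one criterion, one date per prior user and one restated comparison. The downside is slower entry: a prior user on regular injections could wait up to 12 to 16 weeks, which the remaining calendar may not allow. For patients already enrolled, only items 2 to 4 can help.

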#### INCLUSION CRITERIA:

- Patients with focal task-specific dystonia of one or both hands, selectively triggered by performance on a musical instrument.
- Patients must have been evaluated by [name] at the Movement Disorders Division of NYU Langone Hospital as part of their clinical care.
- Patients whose performance on an instrument is directly linked to their occupation.
- Patients must be between the ages of 18 and 80.
- Impairment in musical performance must be visible and demonstrable.

#### EXCLUSION CRITERIA:

- Patients whose dystonia is not severe enough to interfere with musical performance in the opinion of a skilled examiner.
- Patients with unstable medical conditions or psychiatric conditions.

### **c) Patients with a medical condition that precludes them from receiving BoNT injections. Number of Subjects**

This will be a placebo-controlled, double-blind, randomized, cross-over pilot study to assess the efficacy and tolerability of BoNT injections to treat musician's dystonia. The study will enroll a total of 2 patients that will be divided into two groups:

 Mount Sinai	Protocol Title:	A PLACEBO-CONTROLLED, DOUBLE-BLIND, RANDOMIZED, CROSS OVER PILOT STUDY OF THE EFFICACY AND TOLERABILITY OF INCOBOTULINUM TOXIN A (XEOMIN) AS A TREATMENT FOR FOCAL TASK-SPECIFIC DYSTONIA OF THE MUSICIAN'S HAND
	Principal Investigator Name/Contact Info:	[name].
	Primary Contact Name/Contact Info	[name] [contact]
	Date Revised:	10/22/2019
	Study Number:	HS: 13-00822 GCO: 13-1679

- 1) Group 1: Naïve to BoNT treatment (10 patients).
- 2) Group 2: Prior treatment with BoNT (10 patients).

The study anticipates screening 26 patients to enroll 21 who are eligible for randomization.

#### **d) Study Timelines**

There will be 7 or 10 visits depending on which week would be your optimal dosing over the 24-28 week study period. Patients will be seen at weeks 1, 2, 4, 12, 14, 16, and 24, (see attached flow sheet – appendix 1). If patient needs booster dosage at week 2 or 4, patient will be asked to return to have another visit at 4 week after optimal dosing. There will be a total of 7-10 research visits over a 24-28 week period. All visits are expected to last approximately 2-3 hours. The study started in January 2014 and anticipates ending in June 2020. During the study, we may split Visits so that the patient can be seen easily by [name] and not create a hardship for the participant. If the study visit is split, it will mean that [name] assessment will occur prior to the assessment and treatment at [name] location on two consecutive days.

#### **e) Study Endpoints**

##### **Primary Outcome Measures:**

The principal outcome measure will be improvement in musical performance, measured by self-rated questionnaire, quantitative MIDI analysis and blinded high speed video analysis.

##### **Secondary Outcomes Measures:**

Patient reported outcomes will be measured by questionnaires that address adverse events; and modified hospital anxiety depression scale (mHADS), and perceived stress scale to capture impact of anxiety, depression and stress.

Motor strength will be tested using the Medical Research Council (MRC) muscle scale and a dynamometer to document any weakness the treatment may produce as compared to the baseline visit.

 Mount Sinai	Protocol Title:	A PLACEBO-CONTROLLED, DOUBLE-BLIND, RANDOMIZED, CROSS OVER PILOT STUDY OF THE EFFICACY AND TOLERABILITY OF INCOBOTULINUM TOXIN A (XEOMIN) AS A TREATMENT FOR FOCAL TASK-SPECIFIC DYSTONIA OF THE MUSICIAN'S HAND
	Principal Investigator Name/Contact Info:	[name].
	Primary Contact Name/Contact Info	[name] [contact]
	Date Revised:	10/22/2019
	Study Number:	HS: 13-00822 GCO: 13-1679

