## 1) Objectives:

The research question of this exploratory crossover pilot trial is: compared to placebo, does BoNT significantly improve the motor performance and subjective disability of patients suffering from focal task specific dystonia of the musician's hand? Focal task-specific dystonia of the musician's hand is a disorder that frequently impairs or ends the careers of highly skilled performing artists. [name] has personally evaluated more than 170 of these patients over the last decade; clinically and anecdotally, BoNT is often used to treat these musicians, but few studies exist that quantify their motor and subjective improvement or the prevalence of adverse effects. This trial will be performed using BoNT versus placebo in 20 patients with musician's hand dystonia, to refine quantitative measures of performance using Musical Instrument Digital Interface (MIDI) technology and high speed video analysis, demonstrate efficacy and tolerability of BoNT injections, and provide power calculations for a future multi-center double blind clinical trial.

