The statistical analysis will be performed by the investigators with the help of a biostatistician at Mount Sinai research institute, [name]. A total of 20 subjects will be enrolled to this two-treatment (BoNT vs. placebo) crossover study. The probability is 80% that the study will detect a treatment difference at a two-sided 0.05 significance level, if the true difference between the treatments is 0.935 units. This is based upon the assumption that the within-patient standard of the response variable is 1. Although the signal to noise ratio is not optimal due to the small subject size, we believe that this study will be able to detect a significant difference between the study drug and placebo. This is based on reviews of video of robust improvement in treated patients. Keeping the sample size small also allows us to finish recruitment within two years, and to complete all phases of the study by 24 months in order to supple information for planning for a larger definitive study. We hope that the dropout rate will be less than 3%.

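### Motor strength is given only the baseline visit as comparator; the plan should state a within-patient BoNT-minus-placebo comparison

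*Combined protocol and SAP*

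**What the plan says.** Section 5e lists strength, by MRC scale and dynamometer, among the secondary measures. Its purpose is "to document any weakness the treatment may produce as compared to the baseline visit". No other sentence in the documents says what strength will be compared with.

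Section 5f puts MRC and dynamometry in the Visit 1 examination and then repeats a "Brief neurological exam to evaluate for weakness of the targeted muscles and surrounded non-targeted muscles" at the follow-up visits of both cycles. At Visit 5 it allows the second treatment to be deferred in patients with "persistent weakness from the first treatment cycle".

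Section 1 sets BoNT against placebo and includes among the aims to "demonstrate efficacy and tolerability of BoNT injections". The statistical paragraph in section 5h says "A total of 20 subjects will be enrolled to this two-treatment (BoNT vs. placebo) crossover study" and gives one power statement for a response variable that it does not name. It describes no analysis method for any secondary outcome.

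**The concern.** The section 5e sentence is causal: it concerns weakness that the treatment produces. A change from Visit 1 does not isolate that. It also contains learning on the dynamometer, soreness from the needle, variation in effort, and anything else that moves with time. The placebo cycle carries the same influences without the drug and is there to remove them.

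Cycle 2 adds a further difficulty. In a patient who receives BoNT first, weakness that has not resolved by the second injection would, measured against Visit 1, appear as weakness under placebo.

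Weakness is the first risk named in the Brief Summary, tolerability is in the title and the objectives, and the trial is meant to inform a larger one. If the only comparison reported is with baseline, the weakness estimate carried forward would be uncontrolled, although the data for a controlled one will exist. If both comparisons remain open, the choice between them could be made after the data are seen.

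**Working it through.** **Inputs from the documents (section 5h).** N = 20 in a two-treatment crossover. Power: "The probability is 80% that the study will detect a treatment difference at a two-sided 0.05 significance level". Effect size used for that power: 0.935 units, BoNT against placebo. SD: "within-patient standard of the response variable is 1", read here as the within-patient SD. These belong to the unnamed response variable. Their use for strength below is an assumption, with everything expressed in within-patient SD units.

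**Step 1: reproduce the plan's figure.** The standard error of the within-patient difference is SD × √(2/n) = 1 × √(2/20) = 0.316. The noncentrality is 0.935/0.316 = 2.96. With the noncentral t distribution, two-sided 0.05, power is 79.8% on 18 df (period term fitted) or 80.1% on 19 df (simple paired test). The stated 80% is reproduced.

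**Step 2: baseline-only test, no drug effect.** Suppose strength shifts by s between Visit 1 and the later visits for reasons unrelated to the drug, equally in both cycles. BoNT-cycle change from Visit 1 is a difference of two readings, so it has the same standard error of 0.316. The test is a one-sample t on 19 df with noncentrality s/0.316.

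| Assumed shift s (SD) | s/0.316 | Baseline-only test rejects | BoNT-minus-placebo rejects |
|---|---|---|---|
| 0 | 0 | 5.0% | 5.0% |
| 0.1 | 0.32 | 6.0% | 5.0% |
| 0.2 | 0.63 | 9.2% | 5.0% |
| 0.3 | 0.95 | 14.7% | 5.0% |
| 0.5 | 1.58 | 32.4% | 5.0% |

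The last column is constant because s enters both cycles and cancels in the difference.

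**Step 3: the opposite direction.** If the shift is a practice gain and the true strength loss is 0.935 SD, the baseline comparison sees 0.935 − s. Its power falls from 80.1% to 70.7% at s = 0.1, 59.7% at 0.2 and 47.9% at 0.3.

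**Step 4: what the placebo contrast costs.** Assume 10 patients per sequence, and average residual weakness r at the placebo-cycle readings of those who had BoNT first. Their BoNT-minus-placebo difference shrinks by r. Averaged over the two sequences, the contrast shrinks by r/2, and a period term does not remove this. On 18 df:

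| r (SD) | Contrast 0.935 − r/2 | Power |
|---|---|---|
| 0 | 0.935 | 80% |
| 0.2 | 0.835 | 70% |
| 0.4 | 0.735 | 59% |
| 0.6 | 0.635 | 48% |

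**Step 5: the comparisons that are free of this carry-over.** BoNT-cycle change from Visit 1 contains no residue of study drug: in BoNT-first patients Visit 1 precedes all study drug, and in placebo-first patients the preceding cycle was placebo. A first-cycle-only comparison of change from Visit 1 is also free of it, but is between patients. Its standard error is √2 × √(2/10) = 0.632, twice the 0.316 of the crossover contrast.

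**The case against.** The strongest reply is that section 5e describes what is measured and does not prescribe an analysis. Change from baseline can be the variable while BoNT against placebo remains the contrast. Section 1 places the placebo comparison and tolerability in the same statement of aims, and section 5h describes the whole study as BoNT versus placebo. This stands to the following extent. A reader might infer that the plan throws away its own control, or that the trial cannot attribute weakness to BoNT. The documents do not support either reading: nothing excludes the placebo cycle, and strength is collected in both cycles. What remains is that baseline is the only comparator stated, and no other text supplies one.

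A reader might also take strength to be the main tolerability outcome. The plan designates none, and questionnaires on adverse events are listed beside it.

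The third reply is that the placebo contrast is not free of drawbacks. That is correct, as step 4 shows. Optional boosters also move later visits and add visits for some patients only, and muscles and amounts are chosen at each study visit (section 5i), so the visits and muscles to be compared need definition. These points shape the fix without removing the need for it.

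Finally, no significance test on strength is planned, and the 0.935 and SD of 1 are not tied to strength. The percentages are therefore illustrations of a hypothetical test and not properties of the plan.

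**Conclusion.** The point holds as a gap in specification. The plan names the baseline visit as the sole comparator for strength and states no BoNT-minus-placebo comparison, although both cycles supply the data. Change from Visit 1 alone cannot attribute weakness to the drug.

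The possible size runs from negligible to material. False positives for a baseline-only test rise from 6% to 32% as the assumed shift goes from 0.1 to 0.5 within-patient SD, against 5% for the placebo contrast. This rests on a shift common to both cycles, 20 complete patients and no drug effect. If the shift differs between cycles, the contrast needs the period term. The documents give neither a drift nor an SD for strength, so no single value should be quoted as the trial's error rate.

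This is a secondary measure in an exploratory pilot. No primary result, sample size or stated figure depends on it. It is still worth settling before unblinding, because weakness is a leading named risk and the better comparison needs no new data.

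**What to change.** Amend section 5e to state:

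- Change in dynamometer strength will be compared within patient, BoNT minus placebo, with a period term and a 95% CI.
- The visits compared are defined in advance by time since the cycle's first or last injection, with one of the two chosen. The schedule's optional visits four weeks after optimal dosing, with the ordinary four-week visit for patients who had no booster, appear able to support a last-injection definition.
- The muscles entering the comparison are defined, since the selection may differ between cycles.
- MRC loss is tabulated by treatment cycle, BoNT beside placebo.
- Change from Visit 1 is kept as a descriptive summary.
- Visit 5 strength is shown by sequence, so that residual weakness is visible before the second cycle.
- Because residual weakness would bias the contrast toward zero, the BoNT-cycle change from Visit 1 and the first-cycle-only comparison are reported beside it, the latter with its wider interval.

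The cost is a short paragraph and a few added analyses. No patient, visit, measurement or clinical rule changes. The drawback to state openly is the carry-over bias, which these companion summaries expose but do not remove.
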